### 14.3.2 Safety Analysis

#### 14.3.2.1. Adverse Events

AEs will be coded by system-organ-class and preferred term using the most current MedDRA. Events will be recorded starting at study enrollment through 30 days following the last dose of AVID100, and will be tabulated by maximum severity according to the CTCAE (v5.0).

The calculation of AE incidence will be based on the number of patients per AE category. For each patient who has multiple AEs classified to the same category, that patient will be tabulated

\* For the purposes of this study, "enrollment" is defined as patient registration to participate in this trial; at this time the patient's study identification code and dose cohort will be assigned.

under the highest toxicity grade for that AE category. Summary tables will be presented by dose level, seriousness, severity, and relatedness.

During Phase 1a, first-cycle DLTs, AEs leading to death or to discontinuation of study treatment, and SAEs will be evaluated with special attention.

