Safety Assessment	Patients to be monitored throughout the treatment and follow-up period for occurrence of adverse events (AEs) (acute, delayed, and/or cumulative), as well as for changes in clinical status, vital signs (VS), and laboratory data.  Safety Assessments (1) (Within 14 days prior to 1st dose unless otherwise stipulated)
	
 
Medication survey
 
Adverse events (collection of data from 1st dose to 30 days after final dose)
 
Performance status evaluation (ECOG)
 
Vital signs (including temperature, pulse, respiratory rate, BP, and O2 saturation by pulse oximetry)
 
Physical examination (including weight and pulmonary assessment at each visit)
 
Hematologic parameters
 
Serum chemistries
 
Coagulation parameters
 
Urinalyses
 
Anti-drug antibody (ADA) to AVID100 (Central Lab)
 
Pregnancy testing (if applicable) (serum test within 14 days, urine or serum test repeated within 2 working days prior to 1st dose)
 
12-Lead ECGs
 
Safety Assessments (2) (within 28 days [+2 days] prior to first dose of study drug, provided no antineoplastic therapy has been delivered between safety assessment and first dose of study drug)
 
Ophthalmology exam (complete)
 
MUGA scan or Echocardiogram (follow-up ONLY in patients with a history of CHF, or in patients developing clinical findings suggestive of cardiac dysfunction at any point during the study or the follow-up period)
 
Pulmonary function testing (to include spirometry and DLco)
 

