# 6.11. **Duration of Study Follow-Up**

Upon discontinuation of a patient from further treatment with study drug, follow-up assessments will be conducted as detailed below

- End of Treatment (EOT)\* evaluations will be conducted within approximately 10 days following the decision to discontinue the patient from further treatment with study drug.
- 1 Month Follow-up (1M FUP)\* evaluations will be conducted approximately 30 days (+7 days) following the last dose of study drug.

Note: The 1M FUP evaluation should be conducted ≥ 30 days following the last dose of study drug as all patients are to be followed for a minimum of 30 days after study drug discontinuation in order to monitor for the occurrence of suspected AEs that are both serious and unexpected. See **Section 10.3**; Documenting Adverse Events, **Section 10.4**; Reporting SAEs (Including Patient Deaths) and Unexpected AEs, and **Section 10.5**; Required Follow-up of all AEs and SAEs.

\*Given the Q3W dosing frequency, EOT and 1M FUP evaluations may be combined in those situations where scheduling coincides, provided a minimum of 30 days of post-dosing follow-up have been observed.

• If an observed toxicity thought to be associated with study drug has not resolved by the 1M FUP evaluation, an additional follow-up AE assessment will be conducted approximately 3 months following the last dose of study drug, if feasible, in order to confirm that the event has either resolved, returned to baseline status, or been adequately explained and assessed by the Investigator as chronic and/or stable, and that no longer

term deleterious effects have become evident.\* Follow-up may be repeated approximately 6 months following the last dose of study drug, if indicated.

Any patient who develops pulmonary fibrosis will be followed at approximately 3 month intervals for up to 2 years to assess the course of the disease and evaluate potential reversibility of this finding.

In addition, the occurrence of any significant post-therapy event thought to be associated with study drug must be reported to the Sponsor (or designee).

\*To confirm that events have resolved, returned to baseline status, or been adequately explained. Investigator discretion may be used with respect to the method of contact for this AE assessment; clinical events may be followed in writing or by telephone (and documented in writing); an in-person visit will not be required.

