### 10.3. **Documenting Adverse Events**

Information regarding the occurrence of AEs should be elicited through open-ended questioning of the patient, review of physical examination findings, and review of laboratory results.

All AEs (**including SAEs**) are to be detailed in the source documents and accurately recorded on the Adverse Event page of the patient's eCRF. All new events, as well as those that worsen in intensity or frequency relative to baseline, which occur from signing of informed consent\* through the period of protocol-specified follow-up, must be captured. AEs occurring within 30 days after the last dose of study drug must be reported. SAEs, thought by the Investigator to be related to study drug, however, must be reported any time the Investigator becomes aware of such an event, even if this occurrence is more than 30 days after the last dose of study drug.

AE terms should be recorded concisely, using acceptable medical terms, and, when possible, a diagnosis (i.e., disease or syndrome) rather than the component signs and symptoms (e.g., record congestive heart failure rather than dyspnea, rales, and cyanosis). However, signs and symptoms that are considered unrelated or atypical to encountered syndromes or diseases are to be recorded as individual AEs on the eCRF (e.g., if congestive heart failure and severe headache are observed at the same time, each event is to be recorded as an individual AE). The AE should not be recorded as a procedure or clinical measurement (i.e., a laboratory or vital sign), but should reflect the reason for the procedure or diagnosis. For fatal AEs, death is considered to be an outcome of the AE. The cause of death (rather than the term "death") should be recorded as the AE in the eCRFs. AEs terms will be classified using the Medical Dictionary for Regulatory Activities (MedDRA) classification system.

\*Patients who sign informed consent and are subsequently deemed to be screen failures will be followed for the occurrence of SAEs/AEs until it is determined that they are will not be participating in this trial.

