## 10.4. Reporting SAEs (Including Patient Deaths) and Unexpected SAEs

### 10.4.1 24-Hour Requirement for Reporting to the Sponsor

All SAEs, including SUSARs and patient deaths, experienced by the patient from signing of informed consent until 30 days after receiving the final dose of study drug, or any SAE that occurs after 30 days of receiving the final dose of study drug and is believed to be study drug-related, must be promptly reported (within 24 hours of Investigator awareness) even if the experience does not appear to be associated with the study drug or the protocol. Reports will be made by telephone, telefax, or e-mail transmission to the Sponsor or the Sponsor's designee.

Where SAE submissions are made to the Sponsor's Safety Designee, such submissions must then be transmitted by to the Sponsor's Medical Monitor(s). The SAE Form must be transmitted to the Medical Monitor(s) whether full information regarding the event is known or not.

\*Patients who sign informed consent and are subsequently deemed to be screen failures will be followed for the occurrence of SAEs/AEs until it is determined that they are will not be participating in this trial.

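### The adverse event tables close 30 days after the last dose, so drug-related events that start later must be reported but, causes of death apart, have no planned table or listing

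*Combined protocol and SAP*

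**What the plan says.** The analysis rule is in Section 14.3.2.1. Events are recorded from study enrollment "through 30 days following the last dose of AVID100, and will be tabulated by maximum severity", and the same section then calls for summary tables by dose level, seriousness, severity and relatedness. The Trial Synopsis, under Safety Assessment, has the same end point: "collection of data from 1st dose to 30 days after final dose".

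The collection rules go further:

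- Section 10.3 wants new events, and events that worsen from baseline, recorded on the eCRF "through the period of protocol-specified follow-up, must be captured". It wants drug-related serious events reported "even if this occurrence is more than 30 days after the last dose of study drug".
- Section 10.4.1 puts under the 24-hour rule "any SAE that occurs after 30 days of receiving the final dose of study drug and is believed to be study drug-related".
- Section 6.11 reassesses unresolved drug-associated toxicity at about 3 months and, if indicated, at about 6 months. For fibrosis it says: "Any patient who develops pulmonary fibrosis will be followed at approximately 3 month intervals for up to 2 years". It adds that "the occurrence of any significant post-therapy event thought to be associated with study drug must be reported" to the sponsor. Section 7.2.2 repeats the 3-to-6-month and 2-year periods.
- Section 7.4.3 continues imaging after end of treatment in patients with an ongoing response or stable disease, every 3 months in the first year and every 6 months after that. The chest is imaged at each evaluation, partly to look for fibrosis.

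Section 14.3 plans frequency tables of treatment-related events, and listings and tables of causes of death. It states no window for either.

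**The concern.** Safety is a primary objective in both phases (Sections 3.1.1 and 3.2.1). Section 2.4.2 treats pulmonary toxicity as a recognised risk of the drug class and cites one related pneumonitis case in Phase 1a. Section 8 says that patients will be watched for delayed and cumulative toxicity. For such a drug, the late drug-related event is one that a reader of the final report will want to find.

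The protocol arranges to hear about these events, but its only stated tabulation rule leaves them out. The error has one direction: leaving out a late related event, or the later worst grade of an earlier one, can lower the reported incidence or maximum grade but cannot raise it. The recording limit in 14.3.2.1 also does not match the capture period in 10.3, so two data managers could build different databases from the same protocol.

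**Working it through.** The plan has no figure to reproduce. No sample size, power or error rate is involved. The check sets the windows side by side and looks for a table that covers what lies outside the 30 days.

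**Step 1: windows, counted from the last dose.**

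| Rule | Section | End |
|---|---|---|
| Recording and tabulation | 14.3.2.1 | 30 days |
| Capture of new or worsening events | 10.3 | end of protocol-specified follow-up |
| Drug-related serious events | 10.3, 10.4.1 | none |
| Significant drug-associated events after therapy | 6.11 | none |
| Unresolved drug-associated toxicity | 6.11, 7.2.2 | about 3 months, possibly 6 |
| Pulmonary fibrosis | 6.11, 7.2.2 | up to 2 years |

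Taking 3 months as 91 days, 6 months as 182 and 2 years as 730, the tabulation window covers 30/91 = 33%, 30/182 = 16% and 30/730 = 4% of the finite follow-up periods.

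**Step 2: what each kind of event meets in Section 14.**

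- *Onset by day 30, unresolved or followed longer.* The event is already counted. Section 14.3.2.1 does not say whether a higher grade reached after day 30 replaces the grade at day 30, or where resolution and reversibility are shown.
- *Drug-related serious event with onset after day 30, not fatal.* It must be reported (10.3, 10.4.1). It lies outside the 14.3.2.1 window, and no other table or listing in Section 14 is defined for it.
- *Other significant drug-associated event with onset after day 30.* It must be reported (6.11). The gap is the same.
- *Fibrosis first found on a scan after day 30.* The scan is scheduled (7.4.3) and the patient is then followed for up to 2 years (6.11). Section 14.3.2.1 has no place for the event.
- *Death after day 30.* It may appear among the causes of death (14.3), which have no stated window.

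**Step 3: illustration only.** The documents give no rate of late-onset drug-related serious events. If each of the 60 planned Phase 2a patients had an independent chance p of one, the expected number would be 60p and the chance of at least one 1 − (1 − p)^60:

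| Assumed p | Expected | At least one |
|---|---|---|
| 1% | 0.6 | 45% |
| 2% | 1.2 | 70% |
| 5% | 3.0 | 95% |

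Nothing in the documents supports one row over another. The table shows only that a low rate could still produce an affected patient in a study of this size.

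**The case against.** A reader might infer that unresolved toxicity and pulmonary fibrosis are missing from the tables altogether. The documents do not support that. Toxicity reassessed at 3 or 6 months was present by the 1-month visit, and fibrosis that began in the window is tabulated. The long fibrosis follow-up is there to describe course and reversibility.

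A reader might also infer that grades are frozen at day 30. Section 14.3.2.1 does not say so. Section 10.3.1 collects severity, resolution and outcome for every event, so a later worst grade could be carried into the table. What stands is that the text does not settle the question.

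Nor do late deaths vanish, given the causes-of-death summaries. The treatment-related tables in Section 14.3 carry no window of their own, and silence there is not exclusion. Still, 14.3.2.1 is the only analysis rule that sets a window, and a programmer would apply it.

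It can be said that the follow-up named in 10.3 means only the 1-month visit, and 10.3 does go on to ask for reporting of events within 30 days. But 6.11 and 7.2.2 specify longer follow-up, so the phrase is at best ambiguous.

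Section 14.3 also defers detail to a separate SAP, due before database lock. That document could close the gap; the text supplied does not.

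Finally, late events are ascertained less evenly. The 3-month contact is made only where feasible and may be by telephone, and late reports reach the sponsor without a stated eCRF or grading step for the non-serious ones. This is a sound reason to keep them out of the fixed-window tables, but not to leave them undisplayed.

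**Conclusion.** The point holds in a limited form. Drug-related serious events, and other drug-associated events, with onset after day 30 must be reported but have no planned table or listing beyond causes of death. Whether later worsening of an in-window event counts toward its maximum grade is undefined, and 14.3.2.1 and 10.3 disagree on the capture period.

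The direction of any effect is known: reported harm would be too low. Its size is not. The assumed rates in the illustration have no anchor in the documents, and its percentages also presume that every such event would be left out. They should not be quoted as the probability that this trial misreports harm. The documents available show no late drug-related event that has actually been dropped.

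The conclusion rests on reading 14.3.2.1 as the governing rule for all event tables and on the announced SAP not yet having widened it. It is worth correcting before database lock.

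**What to change.** 1. Reconcile Section 14.3.2.1 and the Synopsis with Section 10.3, so that one capture period is stated, with its exceptions for drug-related events.
2. Keep the window to 30 days after the last dose for the all-cause tables.
3. Add a separate, flagged table or listing of drug-related adverse events and serious adverse events with onset after day 30. For each event, show dose level, time since last dose, grade and outcome.
4. State that the maximum grade and final outcome of drug-related events that began within the window include information from the Section 6.11 follow-up, and mark grades reached after day 30.
5. Say in the SAP how late reports received by the sponsor enter the analysis database and are graded.

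The cost is wording in the protocol and SAP and a small amount of extra table work. The reports are already required, although step 5 may need some data handling that is not yet described. Late events will remain less systematically ascertained than in-window events, which is why they are displayed separately. The drug-related figures may become slightly less favourable. Sample size, error rates, dosing, visit schedule and patient management do not change.

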# 3.2. Phase 2a: Dose-Expansion

# 3.2.1 Primary Objective

To further evaluate the safety, tolerability, and preliminary antineoplastic effect\* of AVID100 when administered at the RP2D\*\* and schedule in 3 expansion cohorts of patients with locally advanced/unresectable or metastatic solid tumor malignancies of epithelial origin, that are measurable, and that express the epidermal growth factor receptor (EGFR). The tumor types to be evaluated in these expansion cohorts are metastatic triple-negative breast cancer (mTNBC), squamous cell carcinoma of the head and neck (SCCHN), and squamous histology non-small cell lung carcinoma (Sq-NSCLC).

Note: To be eligible for study enrollment, analytical results documenting EGFR expression positivity by IHC must be documented by a central laboratory in archival FFPE samples obtained from a previous diagnostic or surgical procedure. In the mTNBC cohort results must be 3+ intensity in  $\geq$  50% of tumor cells or  $\geq$  2+ intensity in  $\geq$  75% of tumor cells. In the SCCHN and Sq-NSCLC cohorts results must be 3+ intensity in  $\geq$  50% of tumor cells. If tissue is unavailable, patients must have primary or metastatic tumor sites(s) considered safely accessible for biopsy, and must be willing to undergo tumor biopsy in order to document EGFR expression positivity to verify study eligibility.

Sufficient FFPE tumor tissue from either a prior procedure or a recent biopsy must also be available for submission to a central laboratory for other study-related evaluations as planned per protocol (see **Section 3.2.3**; Exploratory Objective).

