### 6.6.3.3. Rules for Tolerability in Phase 2a

The criteria for tolerability during Phase 1a will apply to Phase 2a Expansion Cohorts. Safety will be reviewed on an ongoing basis to determine if the dose and schedule chosen based on the Phase 1a dose escalation is safe and well-tolerated in expanded populations of patients with the tumor types selected for the expansion cohorts (mTNBC, SCCHN, and Sq-NSCLC). Should it be determined that the dose is not well-tolerated (i.e.,  $\geq 33.3\%$  of patients in an expansion cohort experience a Cycle 1 DLT), the safety of that dose level will be re-evaluated and the next lower dose with established tolerability in Phase 1a will be administered to subsequent patients.

An exception will be the occurrence of toxicity suggesting organ damage (e.g., pulmonary fibrosis, drug-induced liver injury) occurring in  $\geq 2$  patients within an expanded cohort, in which case further accrual to that cohort will be discontinued.

# 6.7. Continued Therapy After Cycle 1

Upon completion of Cycle 1, in the absence of unacceptable toxicity or disease progression, patients may continue receive additional cycles of study drug Q3W ( $\pm$  2 days), unless further delay is required to allow for amelioration of toxicities. Administration of subsequent dosing cycles is allowable at the discretion of the Investigator, provided the patient meets the retreatment criteria listed below. Additional cycles should be initiated as soon as possible, but not longer than 2 weeks after the completion of the previous cycle, if feasible.

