#### 14. STATISTICAL ANALYSIS AND REPORTING OF DATA

### 14.1. Statistical Considerations

The primary objectives of the Phase 1a portion of this trial are to assess the safety, tolerability, DLTs, and, if feasible, the MTD of AVID100 when administered by 2-hour\* IV infusion to patients with a histologically-documented, measurable or non-measurable, locally advanced or metastatic solid tumor malignancy of epithelial origin that is refractory to standard therapy or for which no standard therapy is available. These effects will be assessed by treating patient cohorts with sequentially escalating doses of AVID100. Other studies to be conducted during this trial include characterization of the pharmacokinetic profile of AVID100, and description of the preliminary antineoplastic activity of AVID100 in these same patient cohorts.

In addition, once the MTD is identified, the Phase 2a portion of the trial will enroll patients to 3 expansion cohorts of patients (approximately 60 patients total) with advanced (unresectable or metastatic) malignancies of epithelial origin (tumor types mTNBC, SCCHN, and Sq-NSCLC), and confirmed as expressing the EGFR and with measurable disease, will be entered to further evaluate tolerability and assess the preliminary antineoplastic activity of AVID100 in this patient population.

Data on safety and preliminary activity collected from additional patients added to the Phase 2a expansion cohorts will be summarized with patients treated at that same dose level in the Phase 1a portion of the trial. No tests of statistical inference will be performed.

\*Protocol v5.0: Extended from 1 hour to 1.5 hours due to Grade 3 IRR observed in Cohort 3 (80 mg/m²); effective 20Jul2017 and documented in a study Note to File dated 21Jul2017 (see **Section 2.3.2.1**; AVID100-01: Clinical Experience)

\*Protocol v6.0: Extended from 1.5 hours to 2 hours due to Grade 2 IRRs observed in Cohort 4(120 mg/m2); effective 21Dec2017 and documented in a study Note to File dated 28Dec2017 (see **Section 2.3.2.1**; AVID100-01: Clinical Experience)

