### 14.3.2.2. Laboratory Determinations

Actual values and change-from-baseline values for continuous data from laboratory determinations (serum chemistry, hematology, coagulation studies, and urinalysis) will be presented in listings. Categorical data measurements will be similarly summarized for the actual values. Laboratory measurements will be graded according to CTCAE, when applicable. The frequencies of the highest CTCAE grade observed will be displayed for each AE and for each starting dose level. Laboratory determinations categorized as in or out of normal range will be summarized in some cases using worst-case shift tables. Clinically significant (CS) or not clinically significant (NCS) criteria may be applied for out-of-range values.

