#### 14.3.2.6. Maximum Tolerated Dose

For Phase 1a, a table will be presented showing the MTD as well as a summary of the dose escalation and any subsequent dose reductions.

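### Safety tables grouped only by dose level merge the three Phase 2a expansion cohorts into one column, and no Phase 2a summary of Cycle 1 DLTs or dose reductions is named

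*Combined protocol and SAP*

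**What the plan says.** Four statements in Section 14 set how safety results are grouped.

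- Section 14.3.2.1, adverse events: "Summary tables will be presented by dose level, seriousness, severity, and relatedness". Of these four terms only dose level sorts patients; the other three sort events.
- Section 14.3.2.2, laboratory toxicity: "The frequencies of the highest CTCAE grade observed will be displayed for each AE and for each starting dose level".
- Section 14.1: safety and activity data from the expansion cohorts "will be summarized with patients treated at that same dose level in the Phase 1a portion of the trial".
- Section 14.3.2.1, on the most important events: "During Phase 1a, first-cycle DLTs, AEs leading to death or to discontinuation of study treatment, and SAEs will be evaluated with special attention". Dose reductions appear in Section 14.3.2.6: "For Phase 1a, a table will be presented showing the MTD as well as a summary of the dose escalation and any subsequent dose reductions".

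Elsewhere the protocol treats the expansion cohort as the unit. The Phase 2a primary objective (Section 3.2.1) covers safety, tolerability and preliminary activity "in 3 expansion cohorts of patients with locally advanced/unresectable or metastatic solid tumor malignancies". The Phase 2a tolerability rule (Section 6.6.3.3) is met when at least 33.3% "of patients in an expansion cohort experience a Cycle 1 DLT", and the organ-damage rule in the same section also counts patients within a cohort. Section 6.5.3.1.2 gives every expansion patient the same starting dose, 220 mg/m².

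**The concern.** A table by dose level suits the dose escalation, where dose is what differs between groups. In Phase 2a the dose is planned to be the same for everyone and the tumour type differs. The stated grouping therefore cannot separate the groups that the Phase 2a objective is about. Section 14.1 makes pooling the stated approach, so this is more than silence about a table layout. The activity analysis has its own Phase 2a paragraph (Section 14.3.3.1); the safety analysis has none.

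Two things are at stake in the final report. A toxicity concentrated in one tumour type would be diluted by the other patients in the column. And the quantities that describe tolerability at the chosen dose, Cycle 1 DLTs and dose reductions, have no named Phase 2a summary. Section 2.6 says that few Phase 1a patients received multiple cycles and that the Phase 2a dose may have to be re-evaluated on acute or longer-term tolerability, so Phase 2a dose reductions are directly relevant.

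**Working it through.** The plan states no figure on this point, so there is nothing to reproduce. The check sets the text side by side and then shows how large the dilution could be.

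**Text**

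| Question | Place | Answer |
|---|---|---|
| Unit of the Phase 2a safety objective | 3.2.1 | three expansion cohorts |
| Unit of the Phase 2a tolerability rules | 6.6.3.3 | expansion cohort |
| Patient grouping of AE tables | 14.3.2.1 | dose level |
| Patient grouping of graded laboratory toxicity | 14.3.2.2 | starting dose level |
| Handling of Phase 2a safety data | 14.1 | pooled with Phase 1a at the same dose |
| Starting dose of all expansion cohorts | 6.5.3.1.2 | 220 mg/m² |
| Named summary of Phase 2a Cycle 1 DLTs | Section 14 | none |
| Named summary of Phase 2a dose reductions | Section 14 | none |

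**Inputs for the illustration**

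- Planned cohort sizes: mTNBC 30, SCCHN 15, Sq-NSCLC 15, all approximate (Section 14.2); 60 in total.
- Phase 1a patients evaluated at 220 mg/m²: 6, with no Cycle 1 DLT (Section 2.6).
- Pooled column: 60 + 6 = 66.
- Threshold: 33.3% (Section 6.6.3.3). The smallest count that meets it is 5 of 15 or 10 of 30.

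**Formula.** Let a cohort of size n have x DLTs, let the other 60 − n expansion patients have DLT rate q, and let Phase 1a contribute 0 of 6. Then

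pooled rate = [x + q(60 − n)] / 66.

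The values of q are assumptions; the documents give none.

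| Cohort at the threshold | By cohort | q = 0 | q = 5% | q = 10% |
|---|---|---|---|---|
| SCCHN or Sq-NSCLC, 5/15 | 33.3% | 5/66 = 7.6% | (5 + 2.25)/66 = 11.0% | (5 + 4.5)/66 = 14.4% |
| mTNBC, 10/30 | 33.3% | 10/66 = 15.2% | (10 + 1.5)/66 = 17.4% | (10 + 3.0)/66 = 19.7% |

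In each case a cohort that meets the intolerability criterion appears only within a pooled rate well below it.

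The opposite problem can also arise. If the 33.3% rule is met and later patients start at a lower dose, as Section 6.6.3.3 provides, one cohort is spread over two dose columns. The 220 mg/m² column then holds fewer than 66 patients, and a by-dose table cannot reassemble the cohort.

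**The case against.** **Section 14 does not withhold serious events from Phase 2a.** A reader might infer from the sentence that opens with Phase 1a that SAEs, deaths and discontinuations are summarised for that phase only. The text does not support this. AE tables are split by seriousness with no phase limit, and Section 14.3 promises listings and summary tables of withdrawals and causes of death, again with no phase limit. The sentence adds emphasis for Phase 1a and specifies no DLT table even there. What stands is that these outputs have no cohort grouping.

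**Section 14.3.2.6 is correctly scoped.** It is the MTD table, and the MTD is a Phase 1a endpoint (Section 6.9). It is not a general ban on reporting dose reductions in Phase 2a, and removing its Phase 1a wording would extend an escalation table to patients who were not escalated.

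**Patients are protected during the trial.** The rules in Section 6.6.3.3 work through ongoing review, with prompt reporting of DLTs and dose modifications and monthly Phase 2a teleconferences (Section 6.10). Final tables do not operate them. This is right, and it confines the point to the final analysis.

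**The data can be regrouped.** Patient codes carry the study phase or cohort (Section 6.3.2.3), and the action taken with study drug is recorded for each AE (Section 10.3.1). So it would be too strong to say that cohort results cannot be recovered. That supports the low cost of the fix, but a result that could be derived is not a planned one.

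**A detailed SAP is still to come** (Section 14.3). It may add cohort tables. It is not among the documents, and the only instruction it inherits, in Section 14.1, is to pool.

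**Small cohorts.** With 15 patients the estimates are imprecise: an exact 95% interval for 5/15 runs from roughly 12% to 62%. That is a reason to show n/N, and not a reason to merge cohorts that the objective names separately.

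**Conclusion.** The concern holds for the final safety analysis. The stated grouping puts three cohorts and the 6 Phase 1a patients into one 220 mg/m² column, although the Phase 2a primary objective and tolerability rules are set by cohort. No Phase 2a summary of Cycle 1 DLTs or dose reductions is named. At planned sizes, 5/15 (33.3%) would read as 7.6% with no other DLTs, or 11.0% to 14.4% if the other expansion patients had assumed rates of 5% to 10%. These figures are illustrations. They rest on approximate cohort sizes, full accrual at 220 mg/m² and assumed background rates; they do not forecast the trial's results.

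A reader might also take the Phase 1a check of smoking history, lung function and imaging in SCCHN and NSCLC patients (Section 4.2) as a statement that drug-related lung toxicity is expected to differ by tumour type. It is an entry check to rule out existing pulmonary dysfunction and does not say that. The case for cohort tables does not need it.

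**What to change.** 1. In Sections 14.3.2.1 and 14.3.2.2, state that Phase 2a AEs, SAEs, discontinuations and graded laboratory toxicity will be presented by expansion cohort (mTNBC, SCCHN, Sq-NSCLC). Keep the pooled 220 mg/m² column beside them, since it remains the overall description of safety at that dose.
2. Amend the pooling sentence in Section 14.1 so that the pooled summary is in addition to the cohort summaries.
3. Add a separate Phase 2a sentence: Cycle 1 DLTs as n/N per cohort, optionally with an exact 95% confidence interval as a descriptive measure, and dose reductions and delays by cohort.
4. Leave the Phase 1a MTD table in Section 14.3.2.6 as it is.

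The cost is wording, table shells and extra columns, some with small denominators. The data are already collected, and no dose, accrual rule or safety procedure changes.
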